9.6.2 Laboratory Test Results

Actual values and change from baselines for all chemistry and hematology laboratory parameters will be summarized descriptively for each scheduled visit based on the Safety Analysis Set.

Selected laboratory values will also be categorized according to their NCI-CTCAE (V4.03) toxicity grade. The laboratory parameters of interest for these summaries are:

Hematology	Serum Chemistry	
Hemoglobin (decrease)	Alanine transaminase (ALT) (increase)	Albumin (decrease)
Platelets (decrease)	Aspartate transaminase (AST) (increase)	Uric Acid (increase)
White Blood Cell (WBC, increase, decrease)	Alkaline Phosphatase (increase)	Sodium (increase, decrease)
Absolute Neutrophil Count (ANC, decrease)	Total Bilirubin (increase)	Phosphorus (decrease)
Absolute Lymphocyte Count (increase, decrease)	Creatinine (increase)	Potassium (increase, decrease)
	Calcium (increase, decrease)	Magnesium (increase, decrease)
	Glucose (increase, decrease)	

For hypocalcemia and hypercalcemia, serum calcium will be corrected using the formula:

- *Corrected calcium = Serum calcium + 0.8 * (4 – serum albumin) where serum calcium is recorded in mg/dL and serum albumin is recorded in g/dL.*

Shift tables will be presented for the baseline toxicity grade by the worst on-study toxicity grade and the toxicity grade at the end of treatment for the chemistry and hematology parameters with NCI-CTCAE toxicity grading.

9.6.3 Vital Signs

Actual value and change from baseline for weight and vital sign results including blood pressure, pulse, respiratory rate, and temperature will be summarized at each scheduled protocol time point. The mean pre- and post-carfilzomib SBP and DBP on C1 – 6, C12 and C18 will be presented with average change from pre-to post SBP and DBP summarized for each date. Any clinically significant values as assessed by the investigator will be reported as adverse events.

9.6.4 Physical Measurements

The following physical examination will be summarized over time

- ECOG PS
- Weight
- BSA

9.6.5 Electrocardiogram

The ECG measurements from this clinical study were performed at Screening and as per standard of care for routine safety monitoring, rather than for purposes of assessment of potential QTc effect. No summary of ECG results will be provided.

9.6.6 Echocardiogram

Left ventricular ejection fraction (LVEF) as determined by MUGA Scan or Echocardiogram at baseline, during cycle 2 (for dose evaluation subjects), **and** at End of Treatment will be summarized over time. Changes in LVEF from baseline will be presented descriptively.

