9.2.2.2 Nonhematologic Toxicity

Guidelines for dose modification in the event of nonhematologic toxicities are summarized in **Table 9**.

Table 9 Treatment Guidelines for Nonhematologic Toxicity

Symptom	Recommended Action	
	Lenalidomide	Carfilzomib
Blood and Lymphatic System		
Thrombotic microangiopathy (TMA) Fever, microangiopathic hemolytic anemia, thrombocytopenia, renal failure, neurologic changes		If the diagnosis is suspected, stop lenalidomide and carfilzomib and manage per standard of care including plasma exchange as clinically appropriate. If TMA is confirmed and related to lenalidomide or carfilzomib, permanently discontinue. If the diagnosis of TMA is excluded, lenalidomide and carfilzomib dosing may be resumed at full dose if clinically appropriate.
Cardiac		
Congestive heart failure	Full dose	Any subject with symptoms of congestive heart failure, whether or not drug related, must have the dose held until resolution or return to baseline, after which treatment may continue at a reduced dose, or the subject may be permanently discontinued. If no resolution after 4 weeks, the subject will be withdrawn from all study treatment.
Hypertensive crisis Sustained or persistent SBP \geq 180 mm Hg or DBP \geq 110 mm Hg	Full dose	Hold carfilzomib until resolution to baseline, then resume at 1 dose decrement
LVEF Reduction < 40% or < 55% if the drop is greater than 20% from baseline	Full dose	Hold carfilzomib until LVEF returns to \geq 40% or, if held due to a drop to < 55%, to within 15% of baseline. Resume at 1 dose decrement.
Infections and Infestations		
Infection Grade 3 or 4		Hold both lenalidomide and carfilzomib until systemic treatment for infection is complete. If ANC $>$ 1,000/ μ L, resume both drugs at full dose. If ANC $<$ 1,000/ μ L, follow hematologic toxicities dosage guidelines.
Hepatic Dysfunction and Related Investigations		
Mild liver dysfunction, defined as 2 consecutive values, at least 28 days apart, of: (1) total bilirubin ($>$ 33% direct) $>$ 1x ULN to $<$ 1.5x ULN OR (2) an elevation of AST and/or ALT with normal bilirubin	Full dose.	25% dose reduction. Dose may be re-escalated if liver function tests return to normal and drug-induced hepatotoxicity is excluded.

Page 1 of 3

Footnotes defined on last page of table

Table 9 Treatment Guidelines for Nonhematologic Toxicity (cont'd)

Symptom	Recommended Action	
	Lenalidomide	Carfilzomib
Hepatic Dysfunction and Related Investigations (cont'd)		

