10.1.8 ECHOCARDIOGRAM

A 2-D transthoracic ECHO to assess LVEF will be performed in all subjects at Screening and at EOT. During the Dose-evaluation Component, an ECHO is also required at Cycle 2 Day 15, \pm 7 days. Additional ECHO assessment is only required for subjects who develop clinically significant congestive heart failure.

If transthoracic ECHO is not available, multigated acquisition (MUGA) will be acceptable for LVEF evaluation.

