APPENDIX A SCHEDULE OF STUDY ASSESSMENTS

Assessment	Screening ^a	Baseline ^b	Cycles 1 through 18							EOT ^c	Active Follow-up
			D1	D8	D9	D11	D15	D21	D22		
Informed Consent	X										
Inclusion/exclusion criteria	X										
Medical and treatment history	X										
Time of pre-carfilzomib resting BP and time of dexamethasone administration (Cycles 1-6, 12, and 18)			X	X				X			
Vital signs	X		X	X				X		X	
Post-carfilzomib BP (Cycles 1-6, 12, and 18)			X	X				X			
Physical examination ^d and ECOG Performance Score	X		X							X	
Hematology	X		X	X				X		X	
Full serum chemistry panel ^e	X		X							X	
Abbreviated serum chemistry panel ^f				X				X			
Coagulation		X								X	
ECG (repeat if clinically indicated)	X										
ECHO/MUGA	Dose-evaluation cohorts (Cycle 2 and as clinically indicated)	X						X		X	
	Dose-expansion arms (repeat if clinically indicated)	X								X	

Page 1 of 3

Footnotes defined on last page of table

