APPENDIX A SCHEDULE OF STUDY ASSESSMENTS (CONT'D)

Assessment	Screening ^a	Baseline ^b	Cycles 1 through 18							EOT ^c	Active Follow-up
			D1	D8	D9	D11	D15	D21	D22		
Blood for MRD/NGS (central lab): Baseline; Cycle 8 Day 1; and upon achieving CR or sCR		X	X ^g								
Genomic Biomarkers blood and saliva (optional)		X									
Plasma PK (Cycle 1 only)				X							
Blood for PDn Cohorts 1-2 and first 8 subjects in Arm 3 (Cycle 1 only)			X ⁱ	X ⁱ	X ^j	X ^j					
Questionnaire: patient convenience/satisfaction (Cycles 3 and 18 only)			X								
IV hydration (Cycle 1 only)			X	X			X				
Carfilzomib administration			X	X			X				
Dexamethasone administration ^k	Cycles 1 to 8		X	X			X		X		
	Cycles 9 to 18		X	X			X				
Lenalidomide administration			→								
Adverse events			→								
Concomitant medications			→								

Footnotes defined on last page of table

Page 3 of 3

BP = blood pressure; BSA = body surface area; CR = complete response; ECG = electrocardiogram; ECOG = Eastern Cooperative Oncology Group; EOT = end of treatment; FCBP = females of childbearing potential; FISH = fluorescent in situ hybridization; IV = intravenous (ly); MRD = minimal residual disease; MUGA = multigated acquisition; PD = progressive disease; PDn = pharmacodynamic(s); PK = pharmacokinetic(s); sCR = stringent complete response; SPEP = serum protein electrophoresis; UPEP = urine protein electrophoresis

Details of Assessments are in the protocol body.

- ^a Screening samples can be collected within 21 days of Cycle 1 Day 1.
- ^b It is recommended that baseline samples are collected only after subject is enrolled.
- ^c EOT visit must be scheduled 28 ± 7 days after the last study treatment. EOT ECHO must be performed within 28 ± 7 days after the last study treatment.
- ^d Height is only measured once at screening. BSA is not calculated on Day 1 of Cycle 1 or at EOT visit.
- ^e Full serum chemistry panel will also be collected on Days 8 and 15 of Cycle 1.
- ^f Abbreviated serum chemistry panel will be collected Cycle 2 onwards, Days 8 and 15 (as listed in table).
- ^g After baseline, collect aspirate and blood for MRD only on Day 1 Cycle 8, all subjects, and upon achieving a CR or sCR in all subjects.
- ^h Optional bone marrow aspirate to be collected upon progression of disease in subjects consenting to optional genomic biomarker analysis.
- ⁱ Predose and postdose.

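### In the expansion arms, on-treatment LVEF falls that recover before end of treatment are either unmeasured or left out of the LVEF summary in SAP 9.6.6

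*SAP*

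**What the plan says.** **Schedule.** Protocol 10.1.8 states: "A 2-D transthoracic ECHO to assess LVEF will be performed in all subjects at Screening and at EOT". It adds one on-treatment measurement for part of the study: "During the Dose-evaluation Component, an ECHO is also required at Cycle 2 Day 15", with a window of ± 7 days. MUGA is accepted where transthoracic ECHO is unavailable. Beyond that, "Additional ECHO assessment is only required for subjects who develop clinically significant congestive heart failure". Appendix A has the same fixed visits but words the expansion-arm row differently: "Dose-expansion arms (repeat if clinically indicated"). On timing, Appendix A says: "EOT ECHO must be performed within 28 ± 7 days after the last study treatment".

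**Hold rule.** Protocol Table 9 (section 9.2.2.2) has a row for "LVEF Reduction < 40% or < 55% if the drop is greater than 20% from baseline", separate from its heart-failure row. It calls for carfilzomib to be held and then resumed after LVEF has recovered to a stated level.

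**Analysis.** SAP 9.6.6 covers LVEF "as determined by MUGA Scan or Echocardiogram at baseline, during cycle 2 (for dose evaluation subjects") and at EOT, with changes from baseline presented descriptively. It names no other time point. The SAP amendment history records that summaries at unscheduled visits were taken out of this section and gives no reason for that item, which agrees with the current text.

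**Role of LVEF.** The Protocol synopsis lists change from baseline in ECHO among the safety variables. SAP 9.6.1 lists cardiac failure and cardiomyopathy as events of interest.

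**The concern.** Safety is the primary objective, and LVEF is the study's one quantitative measure of cardiac function over time. In most subjects the summary will rest on two values, one before treatment and one at least three weeks after it ends. Any value obtained between them comes from an unscheduled examination, and SAP 9.6.6 does not use it.

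The omission is selective. A subject whose LVEF fell, whose carfilzomib was held and who resumed after recovery contributes a baseline value and an EOT value, while the value that led to the hold is dropped. A reader of the CSR could then take a flat LVEF table as evidence that function was stable on treatment, when the table was not built to show otherwise. Adverse-event tables give a term and a grade. They do not give the size of the fall or say whether a Table 9 threshold was met.

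**Working it through.** **1. Subjects with a scheduled on-treatment LVEF** (group sizes from SAP 9.1)

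| Group | n | Scheduled on-treatment ECHO |
|---|---|---|
| Arm 1 (NDMM) | 9 | none |
| Arm 2 (RRMM) | 34 | none |
| Arm 3 (NDMM) | 33 | none |
| Cohort 1 (RRMM) | 10 | one, Cycle 2 |
| Cohort 2 (RRMM) | 12 | one, Cycle 2 |
| Cohort 4 (NDMM) | 9 | one, Cycle 2 |

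- Expansion arms: 9 + 34 + 33 = 76; dose-evaluation cohorts: 10 + 12 + 9 = 31; total 107.
- 76/107 = 71.0%; 31/107 = 29.0%.
- 31 is an upper limit. Protocol 5.5 allows Arm 1 subjects who are DLT-evaluable at Cohort 4 dosing to be counted in Cohort 4, and they may have followed the expansion schedule. Subjects who stop early also miss the Cycle 2 measurement.

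**2. Length of the gap for a subject who completes 18 uninterrupted 28-day cycles**

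- Cycle 2 Day 15 is study day 28 + 15 = 43, so the window is days 36 to 50.
- The last lenalidomide dose, Cycle 18 Day 21, is study day 17 × 28 + 21 = 497.
- The EOT ECHO is 21 to 35 days later, days 518 to 532.
- An expansion subject thus has no scheduled LVEF from baseline to day 518 at the earliest. A dose-evaluation subject has none from day 50 at the latest to day 518 at the earliest, at least 468 days. These are full-course figures and are shorter for subjects who stop early.

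**3. What reaches the SAP 9.6.6 summary**

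| On-treatment LVEF fall in an expansion arm | In the LVEF summary? |
|---|---|
| Not measured, recovered by EOT | No |
| Found on an unscheduled ECHO/MUGA, recovered by EOT | No |
| Measured or not, still present at EOT | Yes, as an off-treatment value |

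In dose-evaluation cohorts the same holds, except that a fall present at the Cycle 2 ECHO is included.

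**4. Illustration of scale**

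The documents give no incidence for LVEF falls. Their only detection figure is about 86% for an adverse event of 5% incidence in 38 subjects (Protocol 13.7, SAP 3.2). It reproduces: 1 − 0.95^38 = 0.858.

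The same formula, 1 − (1 − p)^n, is applied to a fall of assumed incidence p that would be visible at a Cycle 2 ECHO:

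| Assumed p | RRMM 70 mg/m², 12 of 46 scheduled | If all 46 scheduled | Arm 3, 0 of 33 scheduled | If all 33 scheduled |
|---|---|---|---|---|
| 2% | 21.5% | 60.5% | 0% | 48.7% |
| 5% | 46.0% | 90.6% | 0% | 81.6% |
| 10% | 71.8% | 99.2% | 0% | 96.9% |

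These are chances of seeing at least one case by scheduled on-treatment ECHO. They describe what the LVEF summary can show and do not argue for a different schedule.

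**5. The Table 9 threshold cannot yet be programmed**

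The second limb reads "< 55% if the drop is greater than 20% from baseline". It does not say whether the 20% is relative or in absolute points. Take an assumed baseline of 60%. A relative drop of more than 20% means LVEF below 0.80 × 60 = 48%. An absolute drop of more than 20 points means below 60 − 20 = 40%, which is already the first limb. The two readings would give different counts.

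**The case against.** Much of the case on the other side stands.

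- **A reader might infer that on-treatment falls in the expansion arms can never appear in the LVEF results, or that every Table 9 LVEF trigger lies outside SAP 9.6.6.** The documents do not support this. EOT values and their change from baseline are summarised for all groups, so a fall that persists to EOT appears, including in a subject who was held and never resumed.
- **A reader might infer that the Table 9 LVEF row contradicts the ECHO schedule.** It does not. A conditional dose-modification row does not itself require a scheduled test. Table 9 has rows for pulmonary hypertension and PRES with no scheduled diagnostic test either. Appendix A also allows a repeat ECHO in expansion arms when clinically indicated, so the row can act on such an examination.
- **Other reporting routes exist.** Cardiac failure and cardiomyopathy events are summarised by preferred term and grade, and treatment-emergent events are listed by subject (SAP 9.6.1). Carfilzomib dose changes and interruptions are counted (SAP 9.6.7). The reason for a hold is recorded in the CRF (Protocol 9.2.2), and individual data go into dataset tabulations (SAP 9.1). None of these is a planned summary of LVEF values, and SAP 9.6.7 specifies no breakdown of holds by reason.
- **The restriction was deliberate, and ECHO is not named in the primary endpoint of Protocol 13.1.1.** Both are true. Leaving unscheduled visits out of a by-visit table is reasonable, because such visits have no common time point. That does not weigh against a worst-value summary, which SAP 9.6.2 already uses for laboratory toxicity grades.
- **The counts are of subjects without a scheduled ECHO, not of hidden declines.** Correct. The documents give no basis for estimating the latter.

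**Conclusion.** The concern holds in a limited form. In 76 of 107 subjects (71%) no on-treatment LVEF is scheduled, and at most 31 (29%) have one value, early in treatment. On-treatment falls that recover before EOT are either unmeasured or, if found on an unscheduled examination, absent from the SAP 9.6.6 summary. Falls still present 21 to 35 days after the last treatment are shown.

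This is a gap in reporting and interpretation, not an error in the SAP's execution of its own text. It rests on reading the three time points in SAP 9.6.6 as exhaustive, which the amendment history supports. How many values or holds are affected cannot be determined from the documents. The remedy is inexpensive and could change the reported cardiac safety result, so it is worth making.

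One textual difference also needs attention. Protocol 10.1.8 requires a further ECHO only for clinically significant congestive heart failure, while Appendix A says to repeat it if clinically indicated. The two passages must be reconciled.

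**What to change.** Add to SAP 9.6.6, using all ECHO and MUGA records, scheduled and unscheduled:

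1. Worst post-baseline LVEF and its change from baseline.
2. Number (%) of subjects meeting either LVEF threshold in Protocol Table 9, separately on treatment and at EOT. The sponsor must first state whether the 20% drop is relative or in absolute points.
3. Number of subjects with any on-treatment LVEF, as the denominator for on-treatment results, by dose-evaluation cohort and expansion arm.

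State in the CSR that asymptomatic LVEF decline was not systematically assessed on treatment in the expansion arms. Wording that says it was not assessed at all would go too far, since clinically indicated examinations may have been done.

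The sponsor should also reconcile Protocol 10.1.8 with Appendix A on the trigger for a repeat ECHO. No clinical rule is proposed here.

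**Cost.** One additional table from records already collected, with no new procedure, plus the clarification of the 20% drop. The drawback is that unscheduled values are clinically driven, so the worst-value figures will look less favourable than the by-visit summary. The table needs a footnote saying so.

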9.6.7 Exposure to Investigational Product

Extent of exposure to all study treatments (carfilzomib, lenalidomide, and dexamethasone) will be summarized for Safety population

- Duration of treatment (weeks) (carfilzomib in combination with lenalidomide and dexamethasone and each component)
 - Defined as the duration (in weeks) from the date of the first dose of any study drug to the date of the last dose of all study drugs + 1
 - Duration of treatment with carfilzomib / lenalidomide / dexamethasone is defined as duration (in weeks) from the date of the first dose of carfilzomib / lenalidomide / dexamethasone to the date of the last dose of carfilzomib / lenalidomide / dexamethasone + 1
- Total number of treatment cycles received (carfilzomib in combination with lenalidomide and dexamethasone and each component)
 - Defined as the total number of treatment cycles in which at least one dose of any study drug is administered.
 - Number of cycles with carfilzomib / lenalidomide / dexamethasone is defined as the total number of treatment cycles in which at least one dose of carfilzomib / lenalidomide / dexamethasone is administered.
- **Number of treatment cycles received (carfilzomib in combination with lenalidomide and dexamethasone and each component) prior to stem cell transplant (SCT) for subjects who had SCT.**

- **Number of treatment cycles received (carfilzomib in combination with lenalidomide and dexamethasone and each component) for subjects who did not have SCT.**
- Number (%) of subjects dosed by cycle (carfilzomib in combination with lenalidomide and dexamethasone and each component)
- Number of doses of carfilzomib / lenalidomide /dexamethasone administered
 - Defined as the total number of non-zero doses of carfilzomib / lenalidomide /dexamethasone respectively, a subject received during the treatment period of the study.
- Cumulative dose received of carfilzomib (mg and mg/m²), lenalidomide (mg) / dexamethasone (mg) across all cycles, defined as the cumulative dose of carfilzomib / lenalidomide / dexamethasone, respectively.
- Average dose of carfilzomib (mg and mg/m²), lenalidomide (mg), and dexamethasone (mg) per administration, defined as the total dose received divided by the number of doses administered
- Relative dose intensity of carfilzomib / lenalidomide / dexamethasone, calculated as the ratio of actual dose intensity to planned dose intensity and expressed as a percent ([Appendix A](#)).
- Number (%) of subjects with doses missed, dose delays, dose changes, and dose interruptions for carfilzomib and dose changes and dose delays for lenalidomide and dexamethasone, respectively.

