5 STUDY DESIGN

This is an open-label, multicenter, Phase 1b, dose-finding study of carfilzomib administered once-weekly in combination with lenalidomide and dexamethasone (KRd) in 28-day cycles to subjects with multiple myeloma.

Subjects may continue to receive study treatment for up to 18 cycles or until 1 or more of the following events occurs:

- Disease progression
- Allogeneic stem cell transplant
- Withdrawal from the study for any reason
- Study termination by the sponsor
- Death

Disease assessments will be conducted at Screening (within 21 days before dosing on Cycle 1 Day 1) and then on Day 1, \pm 3 days, of every cycle beginning with Cycle 2.

Response will be evaluated using the International Myeloma Working Group (IMWG) - Uniform Response Criteria (URC; [Rajkumar, 2011](#); [Appendix C](#)).

NDMM subjects may interrupt study treatment to proceed to hematopoietic stem cell collection, or stem cell collection and ASCT. The investigator will communicate transplant plans with the clinical study team. Upon completion of collection, subjects may resume study treatment (for up to the total of 18 cycles). Study treatment interruption for autologous hematopoietic stem cell collection may not exceed 42 days. Subjects with interruptions longer than 42 days may resume therapy on trial only with the written permission of the

sponsor study medical monitor. Subjects may interrupt study treatment and proceed to ASCT at any time after Cycle 4. Subjects who undergo ASCT may resume study treatment at any time up to posttransplant day 100, as elected by the investigator.

There will be 2 parts in the study.

The first part is the Dose-evaluation Component during which carfilzomib combination regimens will be evaluated ([Table 2](#) and [Figure 1](#)). Approximately 8 dose-limiting toxicity evaluable subjects will be enrolled into each opened Dose-evaluation cohort. Before opening Dose-expansion **arms**, it must be determined that there are not more than 2 dose-limiting toxicities in 8 DLT-evaluable subjects at the dose selected for Dose-expansion.

Dose-expansion **arms** may open once all safety data for at least 1 cycle at maximal dose carfilzomib is reviewed by the CSRC.

[figure not shown]
The second part is the Dose-expansion Component.

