8.4 STUDY DRUG ACCOUNTABILITY

The sponsor (or designee) and the investigator will maintain records of each shipment of investigational product (IP). Upon receipt of IP, the designated recipient at the study site will inspect the shipment, verify the number and condition of the vials, and prepare an inventory or drug accountability record. The records will document shipment dates, method of shipment, batch numbers, product presentation, quantity of vials contained in the shipment, and dispensation to individual subjects using the subject identification number.

Sites will be required to record and document subject compliance regarding lenalidomide and dexamethasone dosing.

Additional details are provided in the IPIM (Investigational Product Instruction Manual).

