9.2.1.1 Carfilzomib

Carfilzomib will be administered once weekly over 30 minutes (approximate) followed by a flush (see IPIM for details) on Days 1 (\pm 2), 8 (\pm 2), and 15 (\pm 2) of each cycle. The dose can be calculated using the subject's actual body surface area (BSA) at baseline; however, dosing adjustments for subsequent actual BSA determinations is allowed per institutional guidelines. Subjects with a BSA > 2.2 m² will receive a dose based upon a 2.2 m² BSA. Dose adjustments must be made for weight gains/losses of $\geq 20\%$ of baseline body weight. Mechanical infusion pumps are recommended but gravity-dependent infusions are permitted if the 30-minute infusion duration can be reliably maintained.

Cohorts 1, 2, and 3

Carfilzomib will be administered at 20 mg/m² on Cycle 1 Day 1 and given once weekly.

Beginning on Cycle 1 Day 8 the carfilzomib dose will be according to the assigned level of 56 mg/m² or 70 mg/m².

Cohort 4:

Carfilzomib will be administered once-weekly at the following dosing schedule: 20 mg/m² on Day 1 of Cycle 1, 56 mg/m² on Day 8 and Day 15 of Cycle 1, and 70 mg/m² on Day 1 of Cycle 2 and beyond.

Carfilzomib infusion must occur at a facility capable of managing hypersensitivity reactions. Subjects will remain at the investigational site under observation for at least 1 hour following each infusion of carfilzomib in Cycle 1.

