9.2.1.2 Lenalidomide

Lenalidomide will be taken once-daily by mouth with or without food. Lenalidomide capsules should be swallowed whole with water. The capsules should not be opened, broken, or chewed. Subjects will be instructed to take the lenalidomide dose at approximately the same time every day. If a planned administration of lenalidomide is missed, it should be taken as soon as possible within the same calendar day with a return to schedule the following day. If a calendar day of dosing is missed, subjects should not make up doses, but should resume the dosing regimen on schedule with the next course. Missed doses must be reported.

For FCBP, nonpregnant state must be documented prior to the first dose of lenalidomide, every week for the first cycle, prior to the start of each subsequent cycle, **and at EOT**.

Subjects must be advised to not donate blood during treatment with lenalidomide and for 1 month following discontinuation of the drug because the blood might be given to a pregnant female subject whose fetus must not be exposed to lenalidomide.

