9.2.1.3 Dexamethasone

Dexamethasone will be taken by mouth or by IV infusion once-daily on Days 1 (\pm 2), 8 (\pm 2), and 15 (\pm 2) for all cycles and on Day 22 (\pm 2) of Cycles 1 through 8. Dexamethasone will be administered at least 30 minutes (but no more than 4 hours) prior to carfilzomib. Subjects receiving dexamethasone IV on Days 1, 8, and 15 may receive dexamethasone orally on Day 22.

9.2.2 *CARFILZOMIB AND LENALIDOMIDE DOSE MODIFICATION GUIDELINES*

Dose reduction levels of carfilzomib and lenalidomide for toxicity management of individual subjects are provided in [Table 5](#) and [Table 6](#), respectively:

Table 5 Dose Decrement for Carfilzomib

Nominal Dose (mg/m ²)	Reduced Carfilzomib Doses (mg/m ²)		
	Dose -1	Dose -2	Dose -3
20	Discontinue		
56	45	36	Discontinue
70	56	45	36

Table 6 Dose Decrement for Lenalidomide

Nominal Dose (mg)	Reduced Lenalidomide Doses (mg)		
	Dose -1	Dose -2	Dose -3
25	15	10	5
10	5	Discontinue	—

Treatment guidelines for specific hematologic toxicities are outlined in [Section 9.2.2.1](#) and nonhematologic toxicities in [Section 9.2.2.2](#). In addition to dose reductions, administration of carfilzomib and/or lenalidomide may be held temporarily in the event of a treatment-related toxicity at the investigator's discretion. When administration of carfilzomib and/or lenalidomide is held, the reason must be documented in the case report form (CRF), and the medical monitor must be notified within 2 business days of the scheduled dose ([Section 9.1](#)).

If either the lenalidomide or carfilzomib dose level is reduced during a given cycle, the reduced dose level will be continued for the next cycle. If the reduced dose level is tolerated for a complete cycle, the subject may, at the investigator's discretion, resume the dose level prior to the reduction at the start of the subsequent cycle.

Carfilzomib or lenalidomide can be discontinued in the event of a treatment-related toxicity that, in the opinion of the investigator, warrants discontinuation. The subject will be considered still on protocol treatment as long as carfilzomib is being administered.

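### SAP 9.6.7 counts dose holds and changes without their reason and lists missed and interrupted doses only for carfilzomib, and SAP 9.6.1 has no table of adverse events leading to a dose reduction or hold

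*SAP*

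**What the plan says.** SAP 9.6.7 ends its exposure summary with one bullet on dose modification: "Number (%) of subjects with doses missed, dose delays, dose changes, and dose interruptions for carfilzomib and dose changes and dose delays for lenalidomide". The sentence goes on to put dexamethasone with lenalidomide. Carfilzomib therefore has four categories (missed, delayed, changed, interrupted) and the other two drugs have two (changed, delayed). The bullet does not split by reason, does not separate reductions from other changes, and defines none of the four terms.

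SAP 9.6.1 ties adverse events to a treatment action only through withdrawal of carfilzomib and listings of events that led to leaving the study or stopping the investigational product, which SAP 5 defines as carfilzomib. No table covers events leading to a reduction or hold of any drug.

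Much of the needed information is collected:

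- Protocol 9.2.2: "When administration of carfilzomib and/or lenalidomide is held, the reason must be documented in the case report form (CRF".
- Protocol 9.2.1.2, on lenalidomide: "Missed doses must be reported".
- Protocol 8.4: "Sites will be required to record and document subject compliance regarding lenalidomide and dexamethasone dosing".
- Protocol 12.2.1.1 makes the action taken one of the attributes the investigator assigns to each adverse event.

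The protocol also allows pauses that have nothing to do with toxicity, in NDMM subjects only. Protocol 5 says "Study treatment interruption for autologous hematopoietic stem cell collection may not exceed 42 days", and it lets a subject who has ASCT resume up to post-transplant day 100. Protocol 5.7 allows for an ASCT interruption of up to 4.5 months.

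**The concern.** A reader of the study report will want to know how often each drug had to be held or reduced because it was not tolerated. The planned counts do not answer that, for two reasons.

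First, a subject who pauses for collection or transplant can fall into the same count as a subject held for toxicity. This affects only the NDMM groups (Arm 1, Cohort 4, Arm 3), which SAP 9.1 presents side by side at different dose levels. Appendix I of the protocol records that on-study transplant came in with amendment 2, after Arm 1 had enrolled, so pause rates may differ between those groups.

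Second, several protocol rules hold lenalidomide and resume it at full dose. Such a hold is not a change of dose, and whether it is a delay depends on a term the SAP leaves open. It may not be counted at all.

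**Working it through.** The plan states no figure on this point, so there is none to reproduce. The check is a reading of the text plus illustrations with assumed rates.

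**1. Which holds can go uncounted.** In Protocol 9.2.2.1 and 9.2.2.2, lenalidomide is held and then resumed at full dose for a first neutropenia (Table 8). The same holds for Grade 3 or 4 infection with an adequate neutrophil count, moderate liver dysfunction, tumor lysis syndrome and Grade 3 or higher pulmonary toxicity (Table 9). For dexamethasone, Table 11 makes hyperglycemia a hold first, with a reduction only if uncontrolled. (Protocol 9.2.2.3 says Grade 3 dexamethasone-related hyperglycemia need not be held. Those two passages must be reconciled, which is a separate matter.)

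None of these is a dose change. SAP 9.6.7 lists missed, delayed and interrupted doses as separate items for carfilzomib, which suggests that a delay is not meant to include the other two. Protocol 9.1 uses the word for late cycle starts. For a missed lenalidomide day, Protocol 9.2.1.2 says "subjects should not make up doses". On that reading, a mid-cycle hold resumed at full dose enters neither of the two lenalidomide categories.

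**2. Mixing with transplant pauses.** Let *t* be the proportion with a toxicity delay or interruption and *a* the proportion pausing for collection or ASCT. Both are assumed and taken as independent, with every pause counted. Arm 3 has n = 33 (SAP 3.1, Table 1).

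Reported rate = 1 − (1 − t)(1 − a). Subjects counted with no toxicity delay = 33 × a × (1 − t).

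| t | a | Reported rate | Counted with no toxicity delay |
|---|---|---|---|
| 30% | 20% | 1 − 0.7 × 0.8 = 44% | 33 × 0.2 × 0.7 = 4.6 |
| 30% | 50% | 1 − 0.7 × 0.5 = 65% | 33 × 0.5 × 0.7 = 11.6 |
| 20% | 10% / 30% / 50% | 28% / 44% / 60% | 2.6 / 7.9 / 13.2 |
| 40% | 10% / 30% / 50% | 46% / 58% / 70% | 2.0 / 5.9 / 9.9 |

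**3. Whether relative dose intensity repairs this.** SAP Appendix A divides dose received by elapsed time from first to last dose. Take an Arm 3 subject who receives every carfilzomib dose for 18 cycles. The cumulative dose is 20 + 2 × 56 + 17 × 168 = 2988 mg/m². Elapsed time without a pause is (17 × 28 + 14 + 14)/7 = 72 weeks. A pause of P days gives relative intensity 504/(504 + P):

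- P = 42 days: 504/546 = 92%
- P = 100 days: 504/604 = 83%
- P = 136.8 days (4.5 months of 30.4 days): 504/640.8 = 79%

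For lenalidomide, with elapsed weeks equal to planned weeks, a 7-day hold gives 77/84 = 91.7% over 4 cycles and 371/378 = 98.1% over 18 cycles. Over a full course, the transplant pause lowers carfilzomib intensity far more than a one-week toxicity hold lowers lenalidomide intensity. Neither figure says how many subjects were held for toxicity.

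**The case against.** The best defense is that this is one descriptive bullet in a phase 1b study with no hypothesis test, and that other summaries cover much of the ground. SAP 9.6.7 reports doses administered, cumulative dose and relative dose intensity for all three drugs, and cycles received before transplant and in subjects without one. SAP 9.2 reports how many subjects had collection or ASCT. Relapsed and newly diagnosed subjects are presented separately. All of that is true, and the adverse event tables themselves are unaffected. But none of these summaries removes pauses from the counts or gives the number of subjects held for toxicity.

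Four stronger readings are tempting, and the documents do not support them.

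- *Lenalidomide holds are omitted.* This is not established. Delays are counted for lenalidomide and dexamethasone, and the sponsor may record a hold as a delay. Toxicities that lead to a decrement are counted as changes.
- *Re-escalations inflate the count.* The bullet counts subjects. Protocol 9.2.2 allows return only to the level held before a reduction, so a re-escalated subject has already been counted.
- *Body-surface-area updates inflate the count.* Protocol 9.2.1.1 says "dosing adjustments for subsequent actual BSA determinations is allowed per institutional guidelines", but that alters the milligrams given and not the assigned mg/m² level. Nothing shows that the SAP would score it as a change.
- *Every paused subject is a false toxicity count.* In Arm 3, 20% to 50% of 33 is 6.6 to 16.5 paused subjects, but at a 30% toxicity rate some of them also have a toxicity delay. The number without one is about 5 to 12.

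It also stands that the hold-reason rule covers carfilzomib and lenalidomide, not dexamethasone and not reductions. The documents do not show that action taken is recorded separately for each drug.

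**Conclusion.** The point holds as a reporting gap that should be closed. The counts ignore the reason although it is recorded for carfilzomib and lenalidomide holds. Missed and interrupted doses are listed for one drug of three. No table links adverse events to a reduction or hold.

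The mixing is confined to NDMM. Its size is unknown, because the documents give no rate for collection, ASCT or toxicity delays. The Arm 3 illustration (44% to 65% reported against a true 30%) assumes independence and that every pause is scored as a delay or interruption. Across the wider assumptions shown, the excess runs from 6 points (46% against 40%) to 40 points (60% against 20%). The lenalidomide and dexamethasone gap depends on what the SAP means by a delay. The conclusion does not reach the adverse event incidence tables, efficacy or the dose-limiting toxicity assessment.

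**What to change.** In SAP 9.6.7:

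- Define missed, delayed, changed and interrupted.
- For each of carfilzomib, lenalidomide and dexamethasone, report the number (%) of subjects with a dose reduction, and the number (%) with a held, missed or interrupted dose. Show reductions separately from other dose changes.
- Split carfilzomib and lenalidomide holds by recorded reason: adverse event, stem-cell collection or ASCT, other.
- For dexamethasone, and for reductions, use the adverse event action taken where the CRF supports it, and say so where it does not.

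In SAP 9.6.1, add tables of TEAEs leading to dose reduction and TEAEs leading to dose hold, by drug where action taken is recorded by drug.

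The cost is SAP wording and a few extra tables, largely from data the protocol already requires. The reported modification rate for lenalidomide and dexamethasone may look less favorable. No treatment rule is touched.
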